20.3.3 Overall Benefit/Risk Conclusion

Eligible participants will be r/r to prior treatments for their disease, have received one prior line of therapy, and for whom a clinical study is the best option (in the opinion of the Investigator) for next treatment based on response and/or tolerability to prior lines of therapy. Furthermore, participants will have varying levels of disease burden at study entry and almost certainly have acquired mutations as part of their disease course. Therefore, there is no guarantee that any participant will derive clinical benefit during this study.

AstraZeneca believes the anticipated benefits that may be afforded to participants with r/r haematological malignancies currently outweigh the identified and potential risks associated with AZD4573 in combination with acalabrutinib.

As described, the study design aims to minimise risks and build on the preliminary efficacy seen to date in the ongoing FTIH study (D8230C00001), reflecting clinical responses in a r/r participant population. Thus, the benefit/risk assessment for administration of AZD4573 with acalabrutinib is considered acceptable for participants with r/r MCL.

For an assessment of benefit and risks pertaining to the conduct of this study during the COVID-19 pandemic, refer to Appendix [A 11](#).

21 OBJECTIVES AND ENDPOINTS – MODULE 2

Objectives and Endpoints for Part A are outlined in [Table 26](#). An additional primary objective was included for Module 2, regarding AZD4573 monotherapy in MCL.

Table 26 Objectives and Endpoints – Module 2

Objectives	Endpoints
Primary	
Part A	

Assess the safety and tolerability of the RP2D of AZD4573 in combination with acalabrutinib (100 mg BID) for participants who are administered AZD4573 monotherapyAssess the safety and tolerability and confirm the RP2D of AZD4573 monotherapy in MCL	
Adverse events (including SAEs), dose modifications, treatment discontinuation due to AE, AESIs, laboratory data, vital signs, and ECG changesAdverse events (including SAEs), dose modifications, treatment discontinuation due to AE, AESIs, laboratory data, vital signs, and ECG changes
Secondary	
Part A	

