	For subsequent occurrences of Grade 3 TLS, further rechallenge and dose level to be discussed with the Medical Monitor.	For subsequent occurrences of Grade 3 TLS, further rechallenge and dose level to be discussed with the Medical Monitor.	
	For events of Grade 4 TLS, discontinue AZD4573.	For events of Grade 4 TLS, discontinue acalabrutinib.	

Table 31 Recommended Dose Modifications for AZD4573 and Acalabrutinib

Event ^a	Occurrence	Action with AZD4573	Action with Acalabrutinib
Non-haematological Toxicities (Except Liver Dysfunction)			
Grade 3 or 4 non-haematological toxicities	1 st occurrence	
Withhold dosing with AZD4573 until the toxicity has resolved to Grade 1, but no longer than 21 days^b.
 
Adequate supportive therapy as per institutional guidelines should be given. AZD4573 therapy may be resumed at the same dose. No dose modification is required.
	
Withhold acalabrutinib until recovery to Grade ≤ 2.
 
Restart acalabrutinib at the same dose level.

	2 nd and subsequent occurrences	
Withhold dosing AZD4573 up to 21 days^b.
 
Adequate supportive therapy as per institutional guidelines should be given.
 
After resolution to Grade 1, reduce dose by one dose level when restarting AZD4573.
 
If no resolution within 21 days discontinue AZD4573^b.
 
In case of subsequent occurrences, dosing may be modified to skip weekly dose(s) (eg, 2 weeks on/1 week off or to 1 week on/1 to 2 weeks off), after discussing with the Medical Monitor.
	
Withhold acalabrutinib until recovery to Grade ≤ 2.
 
Restart acalabrutinib with 1 level dose reduction or discontinue (see Table 30).

Table 31 Recommended Dose Modifications for AZD4573 and Acalabrutinib

Event ^a	Occurrence	Action with AZD4573	Action with Acalabrutinib
Haematological Toxicities			
Grade 3 or 4 neutropenia without fever or infection, lasting > 7 days despite growth factor support	1 st occurrence	Withhold dosing AZD4573 until Grade ≤ 2 or baseline level. Restart at same dose level following resolution.	Withhold acalabrutinib if Grade 4 neutropenia lasting > 7 days until resolution to Grade ≤ 2 or baseline level and then restart at same dose for 1st occurrence .

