Grade 2 Isolated ALT/AST > 3 to $\leq 5 \times$ ULN or Isolated Bilirubin > 1.5 to $\leq 3 \times$ ULN	After 7 days if hepatic enzymes resolve to Grade ≤ 1 , rechallenge at same dose level.	Withhold or continue acalabrutinib (at Investigator discretion, after discussion with the Medical Monitor). To prevent disease progression, monitor disease parameters closely. Monitor ALT, AST, ALP, and bilirubin at least 1x per week. After 7 days if hepatic enzymes appear to be improving and acalabrutinib was withheld, restart acalabrutinib at current dose level.

Event ^a	Action	
	AZD4573	Acalabrutinib
Grade 3 Isolated ALT/AST > 5-20 × ULN	If recovered to Grade ≤ 1 within 7 days, allow rechallenge at same dose level. If not recovered to baseline level within 7 days, discontinue AZD4573.	Withhold or continue acalabrutinib (at Investigator discretion, after discussion with the Medical Monitor). To prevent disease progression, monitor disease parameters closely.
Grade 3 Isolated Bilirubin > 3-10 × ULN	If recovered to baseline level within 96 hours (-2/+12 hours) of the start of the infusion allow rechallenge at same dose level. If not, discontinue AZD4573	Monitor ALT, AST, ALP, and bilirubin at least 1x per week. After 7 days if hepatic enzymes appear to be improving and acalabrutinib was withheld, restart acalabrutinib with 1 level dose reduction or discontinue.
Grade 4^c Isolated ALT > 20 × ULN or Isolated Bilirubin > 10 × ULN	Discontinue AZD4573.	Discontinue acalabrutinib.
Grade 4 Isolated elevation ($\geq 20 \times$ ULN) in AST without concomitant elevation in ALT $\geq 20 \times$ ULN or concomitant elevation in TBL $\geq 2 \times$ ULN that fails to return to baseline level within 7 days from start of dosing	Discontinue AZD4573.	Discontinue acalabrutinib.
Grade 4^c Isolated AST elevation $\geq 20 \times$ ULN without concomitant elevation in ALT $\geq 20 \times$ ULN or TBL $\geq 2 \times$ ULN	1st occurrence If recovered to Grade ≤ 1 or baseline level within 7 days of the start of the infusion allow rechallenge at same dose level	Withhold or continue acalabrutinib (at Investigator discretion, after discussion with the Medical Monitor). To prevent disease progression, monitor disease parameters closely.
	2nd occurrence If recovered to Grade ≤ 1 or baseline level within 7 days of the start of the infusion allow rechallenge with 1 dose level reduction	Monitor ALT, AST, ALP, and bilirubin at least 1x per week. After 7 days if hepatic enzymes appear to be improving and

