Event ^a	Action	
	AZD4573	Acalabrutinib
	3rd occurrence Discontinue AZD4573	acalabrutinib was withheld, restart acalabrutinib at current dose level at the 1st occurrence and with 1 level dose reduction at the 2nd occurrence . Discontinue acalabrutinib at the 3rd occurrence .
Concurrent elevations in ALT, AST, or bilirubin (Please also refer to Appendix E for actions to be taken in the event of PHL)		
ALT or AST $\geq 3 \times$ ULN with TBL $\geq 2 \times$ ULN (PHL) AND INR $\geq 1.5 \times$ ULN (or $\geq 1.5 \times$ baseline if elevated at baseline) of any duration	Discontinue AZD4573.	Discontinue acalabrutinib.
ALT or AST $\geq 3 \times$ ULN with the appearance of fatigue, nausea, vomiting, right upper quadrant pain or tenderness, fever, rash, and/or eosinophilia $> 5\%$	Discontinue AZD4573.	Discontinue acalabrutinib.
ALT or AST $\geq 3 \times$ ULN and TBL $\geq 2 \times$ ULN where TBL does not return to baseline level within 96 hours (-2/+12 hours) from start of dose and/or AST or ALT do not return to baseline level within 7 days from start of dose	Discontinue AZD4573.	Discontinue acalabrutinib.
Grade 3 elevation ($\geq 5 \times$ ULN) in ALT or AST with TBL elevation above baseline level or ULN, but $< 2 \times$ ULN that do not return to baseline level within 7 days	Discontinue AZD4573.	Discontinue acalabrutinib.
ALT and AST $\geq 3 \times$ ULN with concomitant TBL $\geq 2 \times$ ULN, NO increase in INR $\geq 1.5 \times$ ULN (or $1.5 \times$ baseline), and NO fatigue, nausea, vomiting, right upper quadrant pain or tenderness, fever, rash, and/or eosinophilia $> 5\%$	If recovered to Grade ≤ 1 or baseline level within 96 (-2/+12) hours, rechallenge at same dose level ^c	Withhold acalabrutinib until recovered. Once recovered, restart acalabrutinib at same dose.

^a Adverse reactions are graded using National Cancer Institute CTCAE version 5.0. All grades refer to CTCAE grading except for TLS, which uses the Howard modification of Cairo-Bishop criteria ([Howard et al 2011](#)).

- ^b Elevations in ALT or AST are considered isolated if bilirubin remains below Grade 1, and elevations in bilirubin are considered isolated if ALT and AST remain below Grade 1.

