24.9.1 Retreatment Criteria

Retreatment is defined as the first dose of study drug after a significant period of intentional pause in study drug treatment (other than missed doses, eg, study treatment put on hold until resolution of COVID 19)

Retreatment criteria (criteria to be met before participant restarts study drug infusions [and capsules, as applicable]):

All participants:

- 1 Participant has recovered from all treatment-related non-haematological toxicity to CTCAE Grade ≤ 2 .
- 2 Recovery of neutrophils $\geq 1000/\mu\text{L}$ and platelets $\geq 50,000/\mu\text{L}$.
- 3 Participant has recovered from all hepatic toxicity events within the timeframes described in [Table 32](#) above. If biochemical changes in transaminase(s) and total bilirubin are consistent with the definition of Hy's Law, the participant may continue to receive study drug only if all abnormalities have resolved within the timeframes specified in [Table 32](#) above, there are no symptoms of liver injury and INR has not increased above $1.5 \times \text{ULN}$ (or $1.5 \times \text{baseline}$). In these circumstances the participant must be made aware of the unknown potential for liver damage with continued exposure to AZD4573 prior to retreatment. Documentation of continued consent is required.
- 4 Recovery of uric acid to $< \text{ULN}$.
- 5 Recovery of changes in uric acid, potassium, phosphorus, creatinine or calcium, or symptoms suggestive of TLS as defined in [Table 31](#).
- 6 In case of any new deterioration in laboratory values, not fulfilling eligibility criteria and deemed as clinically significant by the Investigator, the Medical Monitor must be contacted to discuss whether AZD4573 dosing can be continued.

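### Table 32 tells sites both to rechallenge and to discontinue AZD4573 for the same liver result in three places, so primary discontinuation and dose-modification counts lack one definition

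*Protocol*

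**What the plan says.** All references are to the Protocol, Module 2.

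**Table 32 (Section 24.9), AZD4573 column**

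- Grade 3 isolated ALT/AST: if recovered to Grade 1 or lower, the cell goes on "within 7 days, allow rechallenge at same dose level. If not recovered to baseline level within 7 days, discontinue AZD4573".
- Grade 4 isolated AST: one row discontinues for an elevation "that fails to return to baseline level within 7 days from start of dosing". The next row covers the same elevation. On the first occurrence, if AST has recovered to Grade 1 or lower, it continues "or baseline level within 7 days of the start of the infusion allow rechallenge at same dose level". The second occurrence uses the same test, with a one-level reduction.
- Concurrent elevations: one row (ALT or AST at least 3 x ULN with TBL at least 2 x ULN) discontinues where "TBL does not return to baseline level within 96 hours (-2/+12 hours) from start of dose", and/or where ALT or AST is not back to baseline within 7 days. The last row (ALT and AST at least 3 x ULN with TBL at least 2 x ULN, no INR rise, no listed symptoms) covers recovery to Grade 1 or lower "or baseline level within 96 (-2/+12) hours, rechallenge at same dose level".

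**Other sections on liver results.** Section 24.2 compares bilirubin with baseline at 96 hours in potential Hy's law (PHL) cases and requires discontinuation if it is still raised. Section 26.1.10.9 requires permanent discontinuation if bilirubin (96 hours) or transaminases (7 days) have not resolved, and does not say what resolved means.

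**Non-hepatic toxicity.** For Grade 3 or 4 non-haematological events, Table 31 says "Withhold dosing with AZD4573 until the toxicity has resolved to Grade 1". The text of 24.9 allows restart at Grade 2 or lower within 21 days. Section 24.9.1 criterion 1 reads "Participant has recovered from all treatment-related non-haematological toxicity to CTCAE Grade" 2 or lower.

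**Endpoints.** Section 21, Table 26 lists "dose modifications, treatment discontinuation due to AE" among the primary endpoints for both primary objectives of Part A.

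**The concern.** In each liver pair, the instruction to rechallenge and the instruction to stop are tied to different recovery thresholds. The two thresholds do not divide participants into two groups; they leave a band in which both instructions apply. One of those instructions is a permanent stop and the other is a further dose of the drug that preceded the liver event.

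This is first a participant-safety matter. It is also a measurement matter. Whether a participant counts as discontinued due to AE, or as having a dose modification, can depend on which line was followed. Those counts feed the assessment of tolerability and the confirmation of the RP2D in MCL. The triggering events are not described as rare: the risk table in Section 20.3.1 calls events meeting PHL criteria very common with AZD4573 monotherapy, although it gives no rate.

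**Working it through.** The protocol tests no hypothesis (Section 27.1) and states no discontinuation figure, so there is no printed number to reproduce. The check is to apply the rules literally.

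**Inputs.** Table 32 prints Grade 1 as ALT/AST up to 3 x ULN and bilirubin up to 1.5 x ULN, without reference to the participant's own baseline. Section 27.2 plans about 12 participants. Section 27.5 has the SRC meet after the first 6 complete Period 1, Cycle 1.

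**1. Grade 3 isolated ALT/AST.** Let b be baseline and x the value at 7 days, both in multiples of ULN. Rechallenge applies if x ≤ 3; discontinue applies if x > b. Both apply when b < x ≤ 3.

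| Baseline b | Grid values of x meeting both instructions |
|---|---|
| 0.5 | 1.0 to 3.0 |
| 1.0 | 1.5 to 3.0 |
| 1.5 | 2.0 to 3.0 |
| 2.5 | 3.0 |

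(Grid step 0.5.) Only x at or below baseline (rechallenge) or above 3 (discontinue) is unambiguous. The neighbouring Grade 3 isolated bilirubin row uses baseline for both outcomes and has no such band.

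**2. Grade 4 isolated AST.** Discontinue applies if x > b; rechallenge applies if x ≤ 3 or x ≤ b. Both again apply when b < x ≤ 3, at the first and second occurrences. At the third, both rows discontinue. The acalabrutinib column splits the same way: discontinue in one row; withhold, continue or restart in the other.

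**3. Concurrent elevations.** Anyone meeting the last row's entry condition (ALT and AST, no INR rise, no symptoms) also meets the earlier row's (ALT or AST). For those participants both instructions apply if, at 96 hours, ALT/AST are at most 3 x ULN and bilirubin is above baseline but at most 1.5 x ULN. Both also apply if everything is at Grade 1 or lower by 96 hours and ALT or AST is still above baseline at 7 days. A participant with only one transaminase raised, an INR rise or symptoms does not meet the last row, so this pair gives no conflict.

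**4. Is there a tie-breaker?** Section 24.9.1 criterion 3 refers back to Table 32. Section 26.1.10.9 leaves resolution undefined. Section 24.2 names baseline, but only for bilirubin in PHL, and does not mention the last row of Table 32. The precedence sentence in Section 23 concerns module against core, not lines within the module.

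**5. Table 31 against 24.9.** After a Grade 3 or 4 non-haematological event that has fallen to Grade 2 within 21 days, Table 31 still withholds AZD4573 and 24.9 permits restart. This is confined to the AZD4573 column for that toxicity class. The acalabrutinib column uses Grade 2 or lower, and the neutropenia and thrombocytopenia rows use Grade 2 or lower or baseline.

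**6. Size.** One participant classified by the other line moves a proportion by 1/n:

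- n = 12: 1/12 = 8.3 points. 0/12 has an exact 95% CI of 0 to 26.5%; 1/12 has 0.2 to 38.5%.
- n = 6 (first SRC review): 1/6 = 16.7 points.

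The share p of participants in the band is not given. If p is assumed, and participants are independent, the chance that at least one is affected is 1 − (1 − p)^n:

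| Assumed p | n = 12 | n = 6 |
|---|---|---|
| 5% | 46% | 27% |
| 10% | 72% | 47% |
| 20% | 93% | 74% |
| 30% | 99% | 88% |

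**The case against.** Several counter-arguments have force.

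- **Section 24.9.1 does not conflict.** A reader might infer a three-way clash on restart grade. But 24.9.1 lists minimum conditions, all of which must hold, and two of them defer to Tables 31 and 32. A participant at Grade 1 satisfies both Table 31 and 24.9.1. This stands.
- **Section 24.9 is general.** The paragraph is framed as a general rule, is permissive, and itself points to Table 31. This reduces the Table 31 issue to a missing statement of precedence; it does not remove it.
- **Sites do not decide alone.** Appendix E 3 requires notifying the Medical Monitor, Section 26.1.7 requires contact for events unresolved at 96 hours, and Table 32 footnote c requires a documented discussion before rechallenge after Grade 4 transaminases or PHL. So it would be too strong to say that the endpoints merely reflect site reading. Consultation does not, however, tell the Medical Monitor which of two printed instructions applies.
- **Endpoint impact is modest.** No test or discontinuation threshold is set, the SRC judges overall safety, and laboratory data are themselves a primary endpoint, so the liver values will be reported either way. An 8.3-point shift also lies well within the sampling error at n = 12. This stands as to size.
- **A large swing cannot be shown.** A reader might infer that the discontinuation rate could move by several tens of points. That needs a count of participants in the band, and the protocol gives none. Section 26.1.10.9 says the events resolve rapidly, and a Grade 3, Grade 4 or PHL event must occur first.
- **Enrolment is halted** (Section 18.5), so fewer than 12 may be treated and the prospective benefit is limited to anyone still dosed. The data already collected still need one definition.

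**Conclusion.** The contradiction is real and sits in the wording of Table 32: the Grade 3 isolated ALT/AST cell, the Grade 4 isolated AST rows and, for participants meeting both entry conditions, the concurrent-elevation rows. It affects participants at Grade 1 or lower but above baseline at the time limit. Nothing in Sections 23, 24 or 26 resolves it. The Table 31 and 24.9 difference is a lesser inconsistency of precedence, and 24.9.1 is a compatible minimum.

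The supportable size is 8.3 points on the discontinuation rate per participant if n = 12, and 16.7 points at a 6-participant review. How many participants are affected is unknown; the probabilities shown rest on assumed shares. The conclusion takes Grade 1 as Table 32 prints it. No sample size or power statement is touched. The point deserves correction because the opposing instructions concern liver safety and feed a primary endpoint, not because a large bias has been demonstrated.

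**What to change.** The sponsor's clinical and safety functions should reconcile the three places in Table 32 with each other and with Sections 24.2 and 26.1.10.9, so that for any liver result the rechallenge and discontinue conditions cannot both be met. Section 26.1.10.9 should say what resolved means. A sentence should state whether Table 31 or the text of 24.9 takes precedence for AZD4573 after Grade 3 or 4 non-haematological toxicity. The choice of threshold and time limit is theirs. A single threshold or time limit across all these sections is not needed, since they cover different toxicities.

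For participants already treated, record which line was applied at each qualifying liver event. Derive recovery (at or below baseline; at Grade 1 or lower) at 96 hours and 7 days from the laboratory values, and tabulate hepatic discontinuations and dose modifications on one stated definition.

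Cost: amendment wording, a letter to sites with participants still on treatment, and derived recovery variables from liver data already planned for collection.

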24.9.1 Retreatment Criteria

Retreatment is defined as the first dose of study drug after a significant period of intentional pause in study drug treatment (other than missed doses, eg, study treatment put on hold until resolution of COVID 19)

Retreatment criteria (criteria to be met before participant restarts study drug infusions [and capsules, as applicable]):

All participants:

- 1 Participant has recovered from all treatment-related non-haematological toxicity to CTCAE Grade ≤ 2 .
- 2 Recovery of neutrophils $\geq 1000/\mu\text{L}$ and platelets $\geq 50,000/\mu\text{L}$.
- 3 Participant has recovered from all hepatic toxicity events within the timeframes described in [Table 32](#) above. If biochemical changes in transaminase(s) and total bilirubin are consistent with the definition of Hy's Law, the participant may continue to receive study drug only if all abnormalities have resolved within the timeframes specified in [Table 32](#) above, there are no symptoms of liver injury and INR has not increased above $1.5 \times \text{ULN}$ (or $1.5 \times \text{baseline}$). In these circumstances the participant must be made aware of the unknown potential for liver damage with continued exposure to AZD4573 prior to retreatment. Documentation of continued consent is required.
- 4 Recovery of uric acid to $< \text{ULN}$.
- 5 Recovery of changes in uric acid, potassium, phosphorus, creatinine or calcium, or symptoms suggestive of TLS as defined in [Table 31](#).
- 6 In case of any new deterioration in laboratory values, not fulfilling eligibility criteria and deemed as clinically significant by the Investigator, the Medical Monitor must be contacted to discuss whether AZD4573 dosing can be continued.

24.10 Intervention After the End of the Study

Treatment with AZD4573 and acalabrutinib may be continued until disease progression or an unacceptable drug-related toxicity occurs as defined in the protocol, or the patient withdraws or is withdrawn from the study for other reasons.

Patients who discontinue AZD4573 may continue to receive acalabrutinib if they are deriving benefit in the opinion of the Investigator. In addition, patients who discontinue acalabrutinib may continue to receive AZD4573 if they are deriving benefit in the opinion of the Investigator.

25 DISCONTINUATION OF STUDY INTERVENTION AND PARTICIPANT DISCONTINUATION/WITHDRAWAL – MODULE 2

25.1 Discontinuation of Study Intervention

See the SoA for data to be collected at the time of intervention discontinuation and follow-up and for any further evaluations that need to be completed.

Please refer to Section [7.1](#) for information on discontinuation of study intervention.

25.1.1 Temporary Discontinuation

Refer to Section [24.2](#) for information on temporary discontinuation and restarting of study intervention.

25.1.2 Rechallenge

Refer to Section [24.9](#) for information on rechallenge with study intervention.

25.2 Patient Withdrawal from the Study

Please refer to Section [7.2](#) for information on participant withdrawal from the study.

In addition for Module 2, participants who experience an AE during the dosing ramp up (Period 1 Weeks 1-3) that result in inability to complete the dosing ramp up will permanently discontinue AZD4573 and exit the study.

25.3 Procedures for Handling Participants Incorrectly Initiated on AZD4573 or Combination Therapy

Please refer to Section [7.3](#) for information on procedures for handling participants incorrectly initiated on AZD4573 or combination therapy.

